## VIII. MISSING DATA

- a. Missing outcome data in the primary outcome analysis will be handled using multiple imputation under the missing-at-random assumption. Intervention effects will be pooled across imputed datasets using Rubin's rules.

## IX. INTERIM ANALYSES

- a. No interim analyses for efficacy are planned.

**X. MULTIPLICITY CONTROL**

- a. No adjustment required.

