## II. OBJECTIVES AND HYPOTHESES

- a. **Primary Objective:** To determine whether assignment to the four arms (placebo, high THC:low CBD, equal THC:CBD, low THC:high CBD) results in a difference in cumulative opioid analgesic dose compared to placebo coupon at 14 weeks.
  - i. **Null Hypothesis ( $H_0$ ):** Participants randomized to vouchers for deeply discounted soft-gel capsules containing high THC:low CBD, equal THC:CBD, or low THC:high CBD will experience a greater reduction in opioid dose compared to vouchers for deeply discounted placebo capsules.
  - ii. **Alternative hypothesis:** Opioid dose and adverse events will differ by randomized voucher arm.
- b. **Secondary Objectives:** We will also measure outcomes with strong associations with cannabis or opioid analgesic use, including pain, substance use, symptoms of mental illness, and potential adverse events). Secondary analyses will be considered exploratory.

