## III. STUDY DESIGN AND RANDOMIZATION

This study is a pragmatic, double-blind, randomized, parallel-group controlled trial.

- a. Allocation ratio: Participants are allocated 1:1:1:1 to each arm.
- b. Randomization method: Block randomization to ensure equal randomization over time. We stratified by history of cannabis use (cannabis naïve, non-daily cannabis use, daily cannabis use), baseline opioid use (chronic opioid use versus sporadic opioid use), and primary pain condition (neuropathic versus non-neuropathic pain). Chronic opioid treatment is defined as prescribed opioids for greater than or equal to 90 overlapping days in the past 182 days.
- c. Blinding: Participants, investigators and outcome assessors are blinded to allocation of vouchers.

Unblinding will occur after database lock and finalization of this SAP.

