## VI. SAMPLE SIZE AND POWER

- a. We based our power analysis on a difference of 10% change in opioid analgesic dose between randomization arms over 14 weeks, which is clinically meaningful.
- b. **Alpha level:** 0.05, two-tailed, and 0/167 to correct for multiple comparisons between four arms.
- c. **Power:** Our sample size estimates incorporate a statistical power of 80% and 90%
- d. **Assumptions:** 15% attrition
- e. **Target sample size:** 276 (69 per arm)

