## VII. STATISTICAL METHODS

- a. **Primary Outcome Analysis:** We will use linear mixed-effects regression analyses (SAS, PROC MIXED) to examine whether assignment to the randomized voucher intervention at enrollment (independent variable) is associated with changes over time in weekly cumulative dose of opioid analgesics in morphine milliequivalents (dependent variable). We will examine intervention and time effects, as well as intervention-by-time interactions. To account for within-participant correlation across repeated weekly observations, we will include a random intercept for participant. We will follow the intention-to-treat principle, including all randomized participants in their originally assigned treatment groups. We will include covariates that differ at baseline or potential moderators, including gender and age. We will use a two-sided alpha of 0.05 and 95% confidence intervals.
- b. **Secondary Outcomes:** Using a similar approach to Aim 1, we will examine whether the initial soft gel capsule dispensed product with different THC/CBD content leads to adverse events. Each adverse event will be included in a separate model. For dichotomous (e.g., cannabis use disorder) or continuous outcomes (e.g., ASI drug subscale score), we will use mixed-effects linear or logistic regression analyses, respectively (SAS, PROC MIXED or PROC NL MIXED) to examine intervention and time effects, as well as intervention-by-time interactions. We will repeat this model using the initial soft gel capsule dispensed product as an instrumental variable to analyze the average effect of each medical cannabis product among those who continued taking the original product. We will also repeat this model using alternative measures of medical cannabis (cumulative dose of THC and CBD).
- c. **Sensitivity Analyses:** To fully understand the intervention effect, we will also conduct per-protocol analyses. If key variables are unequally distributed among randomized arms, we will conduct adjusted analyses.

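### The SAP sizes the trial with a multiplicity-corrected alpha but analyses the primary outcome at 0.05 with no adjustment, so the threshold for success is not fixed

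*SAP*

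**What the plan says.** Four places in the SAP bear on the primary decision threshold.

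- **Section VI.b (sizing):** "0.05, two-tailed, and 0/167 to correct for multiple comparisons between four arms". Section VI.c lists two powers, 80% and 90%, without saying which alpha either belongs to. The effect is "a difference of 10% change in opioid analgesic dose between randomization arms over 14 weeks", with 15% attrition and a target of 276 (69 per arm). No standard deviation is given.
- **Section VII.a (primary analysis):** "We will use a two-sided alpha of 0.05 and 95% confidence intervals". The model examines intervention, time and intervention-by-time effects. No decisive test or contrast is named.
- **Section X:** "No adjustment required", with no reason given.
- **Section II:** the primary objective asks whether assignment "results in a difference in cumulative opioid analgesic dose compared to placebo coupon at 14 weeks", and the hypothesis lists three active products. The exploratory label covers the secondary analyses only: "Secondary analyses will be considered exploratory".

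**The concern.** One section treats the comparisons between arms as needing a corrected alpha. Two others use the full 0.05 and decline any correction. Nothing in the SAP reconciles them, and the primary comparisons are not called exploratory, so they have no exemption on that ground.

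At stake is whether a product can be declared effective. A primary contrast with a p-value between 0.0167 and 0.05 is positive under sections VII.a and X and not positive under the corrected threshold in section VI. That choice should not be open once the data are unblinded. The quoted power is affected too, because a reader cannot tell which figure applies to the threshold that will be used.

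**Working it through.** **Reading the alpha.** As printed, 0/167 is not a valid alpha. 0.05/3 = 0.0167, which is Bonferroni for three comparisons; all six pairs of four arms would need 0.05/6 = 0.0083. I take 0.0167, as an assumption.

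**The plan's sample size.** 276/4 = 69 per arm, and 69 × 0.85 = 58.65 evaluable. In reverse, 58/0.85 = 68.2, which rounds up to 69. The 69 cannot be derived from the 10% effect without a standard deviation, so the target cannot be checked.

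**Family-wise error.** Section III gives equal allocation ("Participants are allocated 1:1:1:1 to each arm"). Two contrasts sharing the placebo arm then have variance 2σ²/n each and covariance σ²/n, so their correlation is 0.5. For k true-null contrasts with two-sided critical value c:

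FWER = 1 − ∫ φ(u) [Φ(√2·c − u) − Φ(−√2·c − u)]^k du

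| Tests | Alpha each | c | FWER |
|---|---|---|---|
| 3 contrasts with placebo | 0.05 | 1.960 | 12.5% |
| 3 contrasts with placebo | 0.0167 | 2.393 | 4.5% |
| 2 remaining null contrasts, one product truly effective | 0.05 | 1.960 | 9.1% |
| All 6 pairs (studentized range) | 0.05 | 1.960 | 20.3% |
| All 6 pairs (studentized range) | 0.0167 | 2.393 | 7.8% |

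As a check, three independent tests at 0.05 would give 1 − 0.95³ = 14.3%; the shared control lowers this to 12.5%. The last row shows that 0.0167 protects the three placebo contrasts but not all six pairs.

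**Power.** For a two-mean comparison under the normal approximation, the standardised signal is δ = z(1−α/2) + z(power). With N, effect and standard deviation fixed, δ is fixed, so a power at one alpha converts directly to the other:

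- 90% at 0.05: δ = 1.960 + 1.282 = 3.242. At 0.0167, Φ(3.242 − 2.393) = 80.2%.
- 80% at 0.0167: δ = 2.393 + 0.842 = 3.235. At 0.05, Φ(3.235 − 1.960) = 89.9%.
- 80% at 0.05: δ = 1.960 + 0.842 = 2.802. At 0.0167, Φ(2.802 − 2.393) = 65.8%.
- 90% at 0.0167: δ = 2.393 + 1.282 = 3.675. At 0.05, Φ(3.675 − 1.960) = 95.7%.

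With 58.65 per arm, the detectable standardised difference is δ√(2/58.65). Treating the 10% effect as 10 percentage points, the implied standard deviation is 10 divided by that difference:

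| Alpha | Power | Difference | Implied SD |
|---|---|---|---|
| 0.05 | 80% | 0.517 | 19.3 |
| 0.05 | 90% | 0.599 | 16.7 |
| 0.0167 | 80% | 0.597 | 16.7 |
| 0.0167 | 90% | 0.679 | 14.7 |

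The two middle rows almost coincide, so one N and one effect can carry both powers, one per alpha. At a single alpha they cannot: 90% needs (3.242/2.802)² = 1.34 times the n of 80% at 0.05, and (3.675/3.235)² = 1.29 times at 0.0167.

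**The case against.** The strongest reply is that section VII.a can be read as one overall test. With four arms, an intervention-by-time interaction is naturally a single joint test, and the alternative hypothesis in section II speaks of dose differing by arm. Such a test at 0.05 has 5% error, and section X would then be defensible. This stands to the extent that the 12.5% is conditional. It does not settle the matter. The SAP names no overall test and no gatekeeping rule, the objective is worded against placebo, and a single overall test would not need the correction in section VI. Unadjusted contrasts after an overall test could still reach about 9% when one product works.

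A reader might also infer that 80% and 90% power cannot both be true. The SAP does not support that, because section VI lists two alphas and the pairing of 90% at 0.05 with 80% at 0.0167 fits one sample size almost exactly. That pairing is itself an inference, as the SAP never states it. Nor can one say that the quoted power belongs wholly to an unused threshold: 0.05 is among the alphas in section VI, and one of the powers may have been computed at it.

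The power figures come from a simple two-mean comparison, not from the weekly mixed model with multiple imputation, so they show how power shifts between alphas and do not verify either value. The odd printing of 0/167 carries little weight alone. The stated purpose of that alpha is clear however it is read.

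**Conclusion.** The contradiction is real and concerns the primary decision rule, so it must be fixed before unblinding. There are two positions stated in three places. Sections VII.a and X agree with each other and conflict with the corrected alpha in section VI; it would overstate the case to count three conflicting answers.

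The 12.5% family-wise error, against 4.5% at 0.0167, assumes three separate active-versus-placebo tests at 0.05, success on any one, equal arms and a shared control. The objective's wording makes this the likeliest reading, but the plan does not fix it.

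On power, the defect is that neither figure is tied to an alpha. Power at 0.0167 is about 80% if the 90% was computed at 0.05, but only about 66% if it was the 80% that was computed at 0.05.

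**What to change.** **Sections VII.a and X.** Name the primary family as the three active-versus-placebo contrasts and hold its family-wise error at 5% two-sided. Any of these would do:

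- 0.0167 per contrast, as sized, with 98.3% confidence intervals (1 − 0.05/3);
- Holm or Dunnett, with intervals that match the chosen procedure;
- an overall test that gates contrasts which are themselves multiplicity-controlled.

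Replace the statement in section X to agree. If active-versus-active pairs will be tested as well, say whether they belong to the family, since 0.0167 does not cover all six pairs.

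**Section VI.** Correct 0/167 to 0.0167 if that is what was meant. Say which power belongs to which alpha, state the standard deviation used, and quote the power at the alpha of the primary analysis.

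**Cost.** SAP wording only, made before unblinding, with no extra participants. The quoted power becomes the less favourable figure.

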**XI. STATISTICAL SOFTWARE**

- a. SAS 9.4

**XII. DATA MONITORING AND BLINDING**

- a. Database lock occurs- after all data cleaning and planned analyses are completed.
- b. Analysis will be performed by study statistician: [name]
- c. Unblinding occurs after database lock
- d. Statisticians are blinded

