## I. INTRODUCTION

This document describes the planned statistical analyses for ReLeaf, a 14-week, pragmatic randomized, double-blind, four-arm parallel-group trial evaluating the effect of discounted vouchers for: 1) a placebo soft-gel capsule product, 2) high THC: low CBD soft-gel capsule product (4.3 mg THC/0.7 mg CBD), 3) equal THC:CBD soft-gel capsule product (2.5 mg THC/2.5 mg CBD), or 4) low THC: low CBD soft-gel capsule product (0.2 mg THC/4.8 mg CBD) on cumulative opioid analgesic use. The ReLeaf Study randomized participants 1:1:1:1 across four arms.

This Statistical Analysis Plan (SAP) was developed prior to unblinding and database lock.

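### Section XII puts database lock after the planned analyses, so results would be seen on data that can still be changed, and the THC/CBD dose models conflict with unblinding after lock

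*SAP*

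**What the plan says.** Section XII.a fixes lock relative to analysis: "Database lock occurs- after all data cleaning and planned analyses are completed". Section XII.c adds: "Unblinding occurs after database lock". Section III.c agrees: "Unblinding will occur after database lock and finalization of this SAP". Section XII.d says "Statisticians are blinded", with no point at which that blinding ends and no mention of masked arm codes. The Introduction gives the timing of the plan itself: "This Statistical Analysis Plan (SAP) was developed prior to unblinding and database lock".

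Two parts of the SAP show what the analyses need. The primary objective in section II.a asks whether assignment "results in a difference in cumulative opioid analgesic dose compared to placebo coupon at 14 weeks". Section VII.b, under secondary outcomes, adds: "We will also repeat this model using alternative measures of medical cannabis (cumulative dose of THC and CBD".

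**The concern.** Lock freezes the data before anyone knows what they show, so that no record can be corrected, queried or reclassified in response to a result. A plan that analyzes first and locks afterwards gives up that safeguard for every analysis. A later reader could not confirm from the SAP that the data were fixed before the results were known.

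The order also bears on the blind. If lock follows analysis and unblinding follows lock, then all planned analyses must be completed by people who do not know the product identities. Any analysis that needs those identities then forces a breach: either the codes are released before lock, against III.c and XII.c, or the analysis is done after lock, against XII.a.

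**Working it through.** No sample size, alpha or power calculation applies. The check is to put the stated milestones in order and see whether that order can be carried out.

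1. **Order of steps.** XII.a gives cleaning, then planned analyses, then lock. XII.c and III.c give lock, then unblinding. Together: clean → analyze → lock → unblind. No other section changes this.

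2. **What the planned analyses are.** Section IX plans no interim efficacy analyses, so the term cannot mean interim looks at efficacy. The SAP describes no blinded data review or data-check analysis that it could mean instead. The Introduction presents the document as the account of the trial's planned statistical analyses, so the natural reading is section VII, which includes the primary mixed model.

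3. **First consequence: unfrozen data.** From step 1, the section VII results exist before lock. The SAP names no earlier freeze, snapshot or change-control rule to take its place.

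4. **Second consequence: which analyses need product identity.**
   - *Primary model (VII.a).* The intervention, time and interaction terms need only group labels. Four arms give 4 × 3 / 2 = 6 pairwise contrasts. All six can be computed under codes A to D, and the three against placebo identified once the codes are opened. Unblinding is not needed to run them.
   - *Adverse events by product (VII.b).* The same holds under masked labels.
   - *Cumulative THC and CBD dose (VII.b).* A dose in milligrams is the number of capsules times the content per capsule. The Introduction gives THC/CBD contents of 4.3/0.7, 2.5/2.5 and 0.2/4.8 mg for the active products. The variable cannot be built without knowing the product. If someone else built it, an analyst who saw both doses could usually read the product from their ratio: 4.3/0.7 = 6.1, 2.5/2.5 = 1.0 and 0.2/4.8 = 0.04. This last step assumes that the doses come from a single study product per participant.

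5. **Result.** Steps 1 and 3 apply to all analyses. The conflict with the blind in step 4 is established only for the THC/CBD dose models.

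**The case against.** The strongest reply is that the primary analysis is workable as sequenced. XII.d is compatible with analysis under masked codes, and masking hides which arm is placebo, which limits any directed change to the data. The primary endpoint also comes from opioids reported as dispensed to the state prescription monitoring program, not from investigator ratings. The dose models are one repeat analysis within secondary analyses that section II.b calls exploratory. Finally, the stray hyphen in XII.a suggests a drafting slip.

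Much of this stands. A reader might infer that no arm comparison is possible before unblinding; the SAP does not support that, because group labels are enough. But the SAP does not state a masked-code procedure, and masked results are still results seen before the data are fixed. Extraction and dose conversion remain open to change even with an external source. A slip is plausible but cannot be shown, and this sentence is the only one that places lock relative to analysis.

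A reader might also infer that the model is left open in scale and covariance. It is not: section VII.a names the outcome unit and a random intercept. Covariate choice does depend on the data ("We will include covariates that differ at baseline or potential moderators, including gender and age"), but lock freezes data and not models, so that is a separate weakness which reordering would not cure. Nor does the SAP support the inference that re-modelling would be unrestricted. The Introduction dates the plan before unblinding and lock, and III.c requires it to be final before unblinding.

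**Conclusion.** The point holds as an internal sequencing error. As written, XII.a lets all planned analyses be run and seen on data that can still be changed, and the THC/CBD dose models of VII.b cannot be reconciled with unblinding after lock. This is a rule stated wrongly, not a detail left to the protocol.

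The first part touches every planned analysis and the second touches one set of secondary models. The size of any bias cannot be computed, and the SAP gives no sign that data would in fact be altered. The target of 276 participants (69 per arm), the alpha and the power are unaffected. The conclusion rests on reading the planned analyses as those of section VII, which sections I and IX support.

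**What to change.** Restate XII.a to d as one sequence:

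1. Data cleaning, done blinded.
2. SAP finalized.
3. Database lock.
4. Release of treatment codes. Alternatively, release masked arm codes first for the arm comparisons, and product identities afterwards for the THC/CBD dose models.
5. Planned analyses.

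Add two statements: when the statisticians' blinding ends, and that any change to the data after lock is documented. Align III.c with the same wording.

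The cost is a few lines of text. The SAP does not show whether lock or analysis has already taken place, so the effect on the schedule cannot be judged from it. If those steps are past, the document should record the order actually followed.
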